5.5.1. Psoriasis Area and Severity Index

The psoriasis area and severity index (PASI) is a system used for assessing and grading the severity of psoriatic lesions and their response to therapy. In the PASI system, the body is divided into 4 regions: the head, trunk, upper extremities, and lower extremities. Each of these areas is assessed separately for the percentage of the area involved, which translates to a numeric score that ranges from 0 (indicates no involvement) to 6 (90%-100% involvement), and for erythema, induration, and scaling, which are each rated on a scale of 0 to 4. The PASI produces a numeric score that can range from 0 (no psoriasis) to 72. A higher score indicates more severe disease.

The Scoring system of PASI:

The scoring system for the signs of the disease (erythema, induration, and scaling) is:

0 = none,

1 =slight,

2 = moderate,

3 =severe, and

4 = very severe.

The scale for estimating the area of involvement for psoriatic lesions is outlined below.

0 = no involvement

1 = 1% to 9% involvement

2 = 10% to 29% involvement

3 = 30% to 49% involvement

4 = 50% to 69% involvement

5 = 70% to 89% involvement

6 = 90% to 100% involvement

To help with the area assessments, the following conventions should be noted:

- a. The neck is considered part of the head.
- b. The axillae and groin are part of the trunk.
- c. The buttocks are part of the lower extremities,

The PASI formula is:

PASI = 0.1(Eh + Ih + Sh) * Ah + 0.3(Et + It + St) * At + 0.2(Eu + Iu + Su) * Au + 0.4 * (El + Il + Sl) * Al

Where E = erythema, I = induration, S = scaling, and A = area.

Listing of PASI will be presented with change from baseline at each of the scheduled timepoints.

5.5.2. Body Surface Area

The body surface area (BSA) score arithmetic mean of the affected skin surface. The most commonly used

method to estimate the BSA of psoriatic lesions is the "rule of nines", which was originally developed for estimating the surface area of burns. It is defined as 9% coverage for the head and neck, 9% for each arm, 9% for the anterior and posterior legs, and 9% for each of 4 trunk quadrants, and 1% for the groin. The area of the palm can be used as a unit of measure which represents approximately 1% of the BSA. The number of patient hand areas affected can then be calculated is a system used for assessing and grading the severity of psoriatic lesions and their response to therapy. The formula of BSA calculation is provided below:

BSA calculation "Rule of nine"

Area of the palm = unit of measure

The palm of the patient's hand "Handprint" represents approximately 1% of the BSA.

This method is defined as:

9% coverage for the head and neck

9% for each arm (=18)

[figure not shown]
9% for the anterior and 9% posterior side of each leg (=36)

9% for each of 4 trunk quadrants (=36)

1% for the genitalia1

The sum of all palms will define the total BSA

Bożek A, et al. Adv Clin Exp Med 2017;26:851-856

Listing of BSA will be presented with change from baseline at each of the scheduled timepoints.

5.5.3. Dermatology Life Quality Index

The dermatology life quality index (DLQI) is a dermatology-specific quality-of-life instrument designed to assess the impact of the disease on a participant's quality-of-life It is a 10 item PRO questionnaire that, in addition to evaluating total quality-of-life, can be used to assess 6 different aspects that may affect quality-of-life: symptoms and feelings, daily activities, leisure, work or school performance, personal relationships, and treatment. The DLQI produces a numeric score that can range from 0 to 30. A higher score indicates more severe disease.

Listing of DLQI will be presented with change from baseline at each of the scheduled timepoints.

5.5.4. Investigator's Global Assessment

The investigator's global assessment (IGA) documents the investigator's assessment of the participant's psoriasis at a given timepoint. Total lesions are graded for induration, erythema, and scaling. The participant's psoriasis is assessed as cleared (0), minimal (1), mild (2), moderate (3), or severe (4). The IGA mod 2011 scale is static, i.e., it referred exclusively to the participant's disease at the time of the assessment and did not compare with any of the participant's previous disease states at previous visits. The scores are: 0 = clear, 1 = almost clear, 2 = mild, 3 = moderate and 4 = severe.

Induration (I) (averaged over all lesions; use the National Psoriasis Foundation Reference card for measurement)

0 = no evidence of plaque elevation

1 = minimal plaque elevation, = 0.25 mm

2 = mild plaque elevation, = 0.5 mm

3 = moderate plaque elevation, = 0.75 mm

4 = severe plaque elevation, > 1 mm

Erythema (E) (averaged over all lesions)

0 = no evidence of erythema, hyperpigmentation may be present

1 = faint erythema

2 = light red coloration

3 = moderate red coloration

4 = bright red coloration

Scaling (S) (averaged over all lesions)

0 = no evidence of scaling

1 = minimal; occasional fine scale over less than 5% of the lesion

2 = mild; fine scale dominates

3 = moderate; coarse scale predominates

4 = severe; thick, scale predominates

 $Total\ Average = (I + E + S)/3$

Average will be calculated in the device but not displayed. Numeric result will be included in data transfer.

Investigator's Global Assessment based upon above Total Average

- 0 = Cleared, except for residual discoloration
- 1 = Minimal majority of lesions have individual scores for I + E + S / 3 that averages 1
- 2 = Mild- majority of lesions have individual scores for I + E + S / 3 that averages 2
- 3 = Moderate majority of lesions have individual scores for I + E + S / 3 that averages 3
- 4 = Severe majority of lesions have individual scores for I + E + S / 3 that averages 4

Note: Scores should be rounded to the nearest whole number.

```
If total \leq 1.49, score = 1; if total \geq 1.50, score = 2.
```

Listing of IGA will be presented with change from baseline at each of the timepoints scheduled.

5.5.5. Pittsburg Sleep Quality Index

The pittsburg sleep quality index (PSQI) is an effective instrument used to measure the quality and patterns of sleep in the older adult. It differentiates "poor" from "good" sleep by measuring 7 domains: subjective sleep quality, sleep latency, sleep duration, habitual sleep efficiency, sleep disturbances, use of sleep medication, and daytime dysfunction over the last month. The participant self-rates each of these 7 areas of sleep. Scoring of the answers is based on a 0 to 3 scale, whereby 3 reflects the negative extreme on the Likert Scale. A global sum of "5" or greater indicates a "poor" sleeper.

The range of values for questions 5 through 10 are all 0 to 3. Questions 1 through 9 are not allowed to be missing except as noted below. If these questions are missing, then any scores calculated using missing questions are also missing. Thus, it is important to make sure that all questions 1 through 9 have been answered. In the event that a range is given for an answer (for example, '30 to 60' is written as the answer to Q2, minutes to fall asleep), split the difference and enter 45.

On May 20, 2005, on the instruction of [name], the scoring of the PSQI was changed to set the score for Q5J to 0 if either the comment or the value was missing. This may reduce the DISTB score by 1 point and the PSQI Total Score by 1 point.

PSQIDURAT DURATION OF SLEEP

PSQIDURAT DURATION OF SLEEP

IF Q4 \geq 7, THEN set value to 0 IF Q4 < 7 and \geq 6, THEN set value to 1 IF Q4 < 6 and \geq 5, THEN set value to 2 IF Q4 < 5, THEN set value to 3

Minimum Score = 0 (better); Maximum Score = 3 (worse)

PSQIDISTB SLEEP DISTURBANCE

IF Q5b + Q5c + Q5d + Q5e + Q5f + Q5g + Q5h + Q5i + Q5j (IF Q5JCOM is null or Q5j is null, set the value of Q5j to 0) = 0, THEN set value to 0

IF Q5b + Q5c + Q5d + Q5e + Q5f + Q5g + Q5h + Q5i + Q5j (IF Q5JCOM is null or Q5j is null, set the value of Q5j to 0) > 1 and < 9, THEN set value to 1

IF Q5b + Q5c + Q5d + Q5e + Q5f + Q5g + Q5h + Q5i + Q5j (IF Q5JCOM is null or Q5j is null, set the value of Q5j to 0) > 9 and < 18, THEN set value to 2

IF Q5b + Q5c + Q5d + Q5e + Q5f + Q5g + Q5h + Q5i + Q5j (IF Q5JCOM is null or Q5j is null, set the value of Q5j to 0) > 18, THEN set value to 3

Minimum Score = 0 (better); Maximum Score = 3 (worse)

PSQILATEN SLEEP LATENCY

First, recode Q2 into Q2new thusly:

IF $Q2 \ge 0$ and ≤ 15 , THEN set value of Q2new to 0

IF Q2 > 15 and ≤ 30 , THEN set value of Q2new to 1

IF Q2 > 30 and ≤ 60 , THEN set value of Q2new to 2

IF Q2 > 60, THEN set value of Q2new to 3

Next

IF Q5a + Q2new = 0, THEN set value to 0

IF Q5a + Q2new \geq 1 and \leq 2, THEN set value to 1

IF Q5a + Q2new \geq 3 and \leq 4, THEN set value to 2

IF Q5a + Q2new \geq 5 and \leq 6, THEN set value to 3

Minimum Score = 0 (better); Maximum Score = 3 (worse)

PSQIDAYDYS DAY DYSFUNCTION DUE TO SLEEPINESS

IF Q8 + Q9 = 0, THEN set value to 0

IF $Q8 + Q9 \ge 1$ and ≤ 2 , THEN set value to 1

IF $Q8 + Q9 \ge 3$ and ≤ 4 , THEN set value to 2

IF $Q8 + Q9 \ge 5$ and ≤ 6 , THEN set value to 3

Minimum Score = 0 (better); Maximum Score = 3 (worse)

PSQIHSE SLEEP EFFICIENCY

Diffsec = Difference in seconds between day and time of day Q1 and day Q3

CONFIDENTIAL – FOIA Exemptions Apply in U.S.

Diffhour = Absolute value of diffsec / 3600

newtib = IF diffhour > 24, then newtib = diffhour - 24

IF diffhour \leq 24, THEN newtib = diffhour

(NOTE, THE ABOVE JUST CALCULATES THE HOURS BETWEEN

GNT (Q1) AND GMT (Q3))

tmphse = (Q4 / newtib) * 100

IF tmphse \geq 85, THEN set value to 0

IF tmphse < 85 and ≥ 75 , THEN set value to 1

IF tmphse < 75 and ≥ 65 , THEN set value to 2

IF tmphse < 65, THEN set value to 3

Minimum Score = 0 (better); Maximum Score = 3 (worse)

PSQISLPQUAL TOTALSLEEP QUALITY

O6

Minimum Score = 0 (better); Maximum Score = 3 (worse)

PSQIMEDS NEED MEDS TO SLEEP

Q7

Minimum Score = 0 (better); Maximum Score = 3 (worse)

PSQI TOTAL

DURAT + DISTB + LATEN + DAYDYS + HSE + SLPQUAL + MEDS

Minimum Score = 0 (better); Maximum Score = 21 (worse)

Interpretation: TOTAL \leq 5 associated with good sleep quality

TOTAL > 5 associated with poor sleep quality

Listing of PSQI will be presented with change from baseline at each of the timepoints.

5.5.6. Alcohol Use Disorders Identification Test

The alcohol use disorders identification test (AUDIT) is a 10-item screening tool developed by the World Health Organization (WHO) to assess alcohol consumption, drinking behaviors, and alcohol-related problems. Both a clinician-administered version and a self-report version of the AUDIT are provided. Participants should be encouraged to answer the questions in terms of standard drinks. A chart illustrating the approximate number of standard drinks in different alcohol beverages is included. A score of 8 or more is considered to indicate hazardous or harmful alcohol use. The AUDIT has been validated across genders and in a wide range of racial/ethnic groups and is well suited for use in primary care settings.

Score of AUDIT:

Scores for each question range from 0 to 4, with the first response for each question (e.g., never) scoring 0, the second (e.g., less than monthly) scoring 1, the third (e.g., monthly) scoring 2, the fourth (e.g., weekly) scoring 3, and the last response (e.g., daily or almost daily) scoring 4. For questions 9 and 10m which only have three responses, the scoring is 0, 2 and 4 (from left to right).

A score of 8 or more is associated with harmful or hazardous drinking, a score of 13 or more in women, and 15 or more in men, is likely to indicate alcohol dependence.

Listing of AUDIT will be presented with change from baseline at each of the timepoints.

5.5.7. The Hospital Anxiety and Depression Scale

The hospital anxiety and depression scale (HADS) measures anxiety and depression which commonly coexist in a general medical population of participants. The HADS focuses on non-physical symptoms so that it can be used to diagnose depression in people with significant physical ill-health. The questionnaire comprises 7 questions for anxiety and 7 questions for depression and takes 2-5 minutes to complete. Although the anxiety and depression questions are interspersed within the questionnaire, they are scored separately, and cut-off scores are available for quantification. The HADS questionnaire has been validated in many languages, countries and settings, including general practice and community settings.

Listing of HADS will be presented with change from baseline at each of the timepoints.

5.6. Other Safety Analyses

All safety analyses will be based on the safety analysis set based on actual intervention received, unless otherwise specified.

Missing safety data will generally not be imputed. Safety assessment values of the form of "<x" / " \le x" (ie, below the lower limit of quantification) or "> x" / " \ge x" (ie, above the upper limit of quantification) will be imputed as "x" in the calculation of summary statistics but displayed as "<x" / " \le x" or ">x" / " \ge x" in the listings.

For all continuous safety variables, descriptive statistics by Nicotine use, non-Nicotine use and Total group will include the N, mean, standard deviation, median, minimum, and maximum. Categorical variables will be summarized by Nicotine use, non-Nicotine use and Total group using frequency counts and percentages.

5.6.1. Extent of Exposure

The number and percentage of participants who receive study intervention (guselkumab) will be summarized. The number and percentage of participants will also be summarized by visit of week.

Descriptive statistics for duration of study intervention (N, mean, SD, median, and range (minimum, maximum)) will be summarized. Participant-years of intervention are calculated as days of intervention/365.25. Participant-years will be presented by Nicotine use, non-Nicotine use and Total group.

Duration of intervention will be summarized in the following duration categories:

- <4 weeks,
- 4-<12 weeks,

- 12-<16 weeks,
- 16-<20 weeks,
- 20-<28 weeks within a study intervention

Cumulative duration of intervention >= 4 weeks, >= 12 weeks, >= 16 weeks, >= 20 weeks, >= 28 weeks will be summarized.

Study intervention duration is defined as (date of last dose of study intervention – date of first dose of study intervention) +1.

Total dosing days of intervention is defined as the total number of days that study intervention was administered to the participant (excluding days off study intervention).

The number (%) of participants with a dose not administered will be summarized by Nicotine use, non-Nicotine use and Total group and visit of week. Reasons for doses not administered will also be summarized by visit of week.

The number (%) of participants with a study intervention modification prior to injection will be summarized by Nicotine use, non-Nicotine use and Total group and week of visit. A similar summary will be presented for study intervention modification during the injection.

Descriptive statistics will be presented for the following parameters:

- Number of injections
- Cumulative total dose
- Mean daily dose

The mean daily dose of study intervention is calculated as (sum of total daily dose during the intervention phase)/total dosing days of intervention.

Study intervention compliance will be summarized descriptively. See Appendix 7 for further details.

5.6.2. Adverse Events

The verbatim terms used in the case report form (CRF) by investigators to identify adverse events (AEs) will be coded using the latest version of Medical Dictionary for Regulatory Activities (MedDRA) (System Organ Class and Preferred Term).

Any AE occurring at or after administration of adenosine or the initial administration of study intervention (guselkumab) through the day of last dose within the study phase plus 12 weeks or the date of the Final Safety visit, whichever is the latest, is considered to be treatment emergent adverse event (TEAE). If the event occurs on the day of the initial administration of study intervention, and either event time or time of administration are missing, then the event will be assumed to be TEAE. If the event date is recorded as partial or completely missing, then the event

will be considered to be TEAE unless it is known to be prior to the first administration of study intervention based on partial onset date or resolution date. All reported TEAEs will be included in the analysis.

For each adverse event, the number and percentage of participants who experience at least 1 occurrence of the given event will be summarized by Nicotine use, non-Nicotine use and Total group.

Any usual pharmacodynamic actions and expected effects of adenosine administration (refer to Appendix 6.11) of CFR assessment are not considered as AEs

Summary tables will be provided for TEAEs.

The incidence of other TEAEs of special interest will be summarized. See Appendix 8 for list of adverse events in each category.

Listing of all serious adverse events (SAEs) will be provided along with abnormalities of laboratory, vital signs, and other physical observations.

Deaths will be displayed by actual intervention received. Frequencies for the following parameters will be included in the summary table:

- Number of participants who died
- Cause of death
- Relationship to study intervention (yes/no)

A listing of participants who died will be provided.

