## 1.2. Schema

Figure 1: Schematic Overview of the Study

= Guselkumab 100 mg s.c.

= Cardiology Assessments (cfPWV, GLS and CFR)

= Biomarker Assessments

Visit Window between Screening Visit 1 and Screening Visit 2 = maximum of 2 weeks
Visit Window between Screening Visit 2 and Week 0 = minimum of 2 weeks and maximum of 4 weeks
CFR, GLS and cfPWV measurements at Week 0 will be considered as the baseline measurements

 $cfPWV = carotid-femoral\ pulse\ wave\ velocity;\ CFR = coronary\ flow\ reserve;\ GLS = global\ longitudinal\ strain;\ PE = Primary\ Endpoint;\ S1 = Screening\ Visit\ 1\\ (Dermatology\ Assessments);\ S2 = Screening\ Visit\ 2\\ (Cardiology\ Assessments);\ SE = Secondary\ Endpoint$ 

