#### Footnotes:

- a. The Final Efficacy Visit should occur 4 weeks after the last dose of the guselkumab within the study. If a participant permanently discontinues guselkumab before Week 28, the Final Efficacy Visit should take place at the time of discontinuation, or as soon as possible, and all assessments scheduled for the Final Efficacy Visit should be performed.
- b. The participant should return for a Final Safety Visit, 12 weeks after the last guselkumab dose. For participants opting to receive commercially available guselkumab after Week 28, the first dose of guselkumab outside the study (Week 36) should be considered as the Final Safety Visit.
- c. Administered at the site by health care professional (HCP) at Week 0. Subsequent doses may be self-administered at the site under supervision up to Week 28.
- d. BMI calculation is done automatically in the eCRF at each time-point when the weight is measured.
- e. Women of childbearing potential who are dosed at the clinic must have a negative serum pregnancy test at Screening Visit S1 and a negative urine pregnancy test at all other visits. Additional serum or urine pregnancy tests may be performed, as determined necessary by the investigator or required by local regulations, to establish the absence of pregnancy at any time during the participation in the study.
- f. Urine nicotine test to be done before any cardiology measurements (cfPWV, GLS and CFR). CFR should be conducted regardless of a positive urine nicotine test.
- g. At the Week 16 and Week 32 visits, participants who have been fasting for the lipid and metabolic panel are permitted to have a non-caffeinated drink prior to the cardiology assessments. Cardiology assessments (cfPWV, GLS, CFR and other assessments) must be performed at the same lab using the same machines and software, and preferably by the same cardiologist/technician at every visit. If CFR measurement is unsuccessful, ie, if the acoustic window of the coronary artery cannot be properly found, 2 attempts to measure a CFR can be made on different days. In such cases, the visit window can be extended by 7 additional days (CFR visit window=-7/+14 days). Guselkumab must not be administered at Week 0 before a CFR measurement is successfully obtained.

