## 3. OBJECTIVES AND ENDPOINTS

Objectives	Endpoints			
Primary				
To evaluate the effect of guselkumab on CFR measured by transthoracic doppler-echocardiography, in participants with moderate-to-severe psoriasis and intermediate cardiovascular risk*.	• Change from baseline † in CFR at Week 32.			
Secondary				
To evaluate the short-term effect of guselkumab on CFR measured by transthoracic doppler-echocardiography, in participants with moderate-to-severe psoriasis and intermediate cardiovascular risk.	Change from baseline in CFR at Week 16.			
To evaluate the effect of guselkumab on GLS as a surrogate marker of left ventricular function in participants with moderate-to-severe psoriasis and intermediate cardiovascular risk.	
 
Change from baseline in GLS at Week 32.
 
Change from baseline in GLS at Week 16.
 
			
To evaluate the effect of guselkumab on arterial stiffness in participants with moderate-to-severe psoriasis and intermediate cardiovascular risk.	
 
Change from baseline in cfPWV at Week 32.
 
Change from baseline in cfPWV at Week 16.
 
			
To evaluate the effect of guselkumab on CFR among participants in the different CFR categories.	
 
Change from baseline in CFR at Week 16 and Week 32 among participants with CFR in the ranges of 2 to 2.49, 2.5 to 3, and 3.01 to 3.5 at baseline.
 
			
To evaluate the effect of guselkumab on surrogate CV risk markers among nicotine users and non-users in the participant population.	
 
Change from baseline in CFR at Week 16 and Week 32 among nicotine users and non-users.
 
Change from baseline in GLS at Week 16 and Week 32 among nicotine users and non-users.
 
Change from baseline in cfPWV at Week 16 and Week 32 in nicotine users and non-users.
 
			
To assess the safety and tolerability of guselkumab in participants with moderate-to-severe plaque psoriasis and intermediate cardiovascular risk.	Rate of AEs among participants treated with guselkumab.			

\* Intermediate cardiovascular risk defined by CFR ≥2 and ≤3.5 at Screening Visit S2.

**Abbreviations:** AE= Adverse event; cfPWV = carotid-femoral pulse wave velocity; CFR= Coronary Flow Reserve; GLS: Global Longitudinal Strain

The G-CARE study will also investigate the following exploratory objectives:

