5.4. Secondary Endpoint(s) Analysis

5.4.1. Key Confirmatory Secondary Endpoint(s)

The key secondary endpoints include the following at Week 16 and Week 32:

- Change from baseline in CFR at Week 16
- Change from baseline in absolute GLS at Week 16 and Week 32.
- Change from baseline in carotid-femoral pulse wave velocity (cfPWV) at Week 16.
- Change from baseline in cfPWV at Week 32.
- Change from baseline in CFR at Week 16 and Week 32 among participants with CFR in the ranges of 2 to >2.75 and ≤ 2.75 to 3.5 at baseline.
- Change from baseline in CFR at Week 16 and Week 32 among nicotine users and non-users.
- Change from baseline in absolute GLS at Week 16 and Week 32 among nicotine users and non-users.
- Change from baseline in cfPWV at Week 16 and Week 32 in nicotine users and nonusers.
- Rate of Adverse Events (AEs) among participants treated with guselkumab at Week 16 and Week 32.

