5.6.2.1. Imputation Rules for Missing Adverse Event Date/Time of Onset

5.6.2.1.1. Treatment-emergent AEs

AEs with completely missing onset dates will be considered as treatment-emergent (avoiding under reporting of treatment-emergent AEs). AEs with partially missing onset dates will also be included as treatment-emergent when the month (if it exists) and the year occur on or later than the month and year of the initial study treatment date.

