6.2. Appendix 2 Changes to Protocol-Planned Analyses

The Safety Analysis Set is different in the Protocol.

Safety analysis set defined in the protocol as "All enrolled participants who receive at least 1 dose of guselkumab." Whereas in SAP we have modified the definition as "The safety analysis set includes all participants who received at least 1 dose of adenosine and guselkumab".

The Safety Analysis Set will likely contain more participants than the FAS. It would not be appropriate to define the safety analysis set as participants receiving at least one dose of guselkumab. It is necessary to also capture possible safety related information starting with the first assessment of the Coronary Flow Reserve at visit S2, because it involves use of intravenous Adenosine.

All enrolled participants who receive at least 1 dose of guselkumab, while it is "The full analysis set (FAS) includes all participants who received at least 1 dose of guselkumab." in the current SAP.

In Protocol the primary and secondary efficacy endpoints are performed at Week 32 for CFR, GLS and cfPWV, while in SAP it is appropriately defined to be completed at Final Efficacy Visit (Week 32) as per Table 2. The primary and secondary efficacy endpoints will be analyzed at Final Efficacy Visit (Week 32) with the definition applied as per Table 2 for the last dose after premature termination of the study.

In the protocol The Final Efficacy Visit (Week 32) should occur 4 weeks after the last dose of the guselkumab within the study. Whereas in SAP, following the premature termination of the study 4 to 8 weeks after the last dose of guselkumab within the treatment phase will be used.

In the protocol for participants who prematurely discontinues guselkumab before Week 28, the Final Efficacy Visit (Week 32) should take place at the time of discontinuation, or as soon as possible, and all assessments scheduled for the Final Efficacy Visit (Week 32) should be performed, whereas in the SAP for participants who permanently discontinue guselkumab before Week 28, the date of discontinuation will be used.

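### The SAP's treatment-emergent window opens at the S2 adenosine infusion, so AEs with onset before any guselkumab enter the guselkumab AE rate, while the partial-date rules anchor on first guselkumab

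*SAP*

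**What the plan says.** The protocol's safety endpoint (section 3) is "Rate of AEs among participants treated with guselkumab". SAP section 5.4.1 lists it as "Rate of Adverse Events (AEs) among participants treated with guselkumab at Week 16 and Week 32".

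SAP section 5.6.2 defines a treatment-emergent AE as "Any AE occurring at or after administration of adenosine or the initial administration of study intervention (guselkumab) through the day of last dose". To this it adds a further 12 weeks, or the time to the Final Safety Visit if that is later. All TEAEs go into the analysis, summarised by nicotine group and in total. Usual and expected adenosine effects are not AEs. SAP Appendix 2 explains that safety information is wanted "starting with the first assessment of the Coronary Flow Reserve at visit S2, because it involves use of intravenous Adenosine".

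The protocol schema gives the spacing: "Visit Window between Screening Visit 2 and Week 0 = minimum of 2 weeks and maximum of 4 weeks". A footnote to the Schedule of Activities adds "Guselkumab must not be administered at Week 0 before a CFR measurement is successfully obtained", so all time from S2 to the Week 0 CFR is free of guselkumab. Protocol section 8.3.1 collects AEs from consent.

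The rules for incomplete dates use a different anchor:
- **SAP 5.6.2:** an AE with a partial or missing date "will be considered to be TEAE unless it is known to be prior to the first administration of study intervention", judged from the partial onset date or the resolution date.
- **SAP 5.6.2.1.1:** "AEs with partially missing onset dates will also be included as treatment-emergent when the month (if it exists) and the year occur on or" after those of initial study treatment.
- **SAP 5.6.2.1.2:** the imputation matrix refers only to the treatment start date (TRTSDT). It contains no adenosine date.

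**The concern.** An infection or injury ten days before the first injection cannot be an effect of guselkumab. Under the SAP definition it is nevertheless a TEAE and is tabulated with on-drug events in the endpoint meant to describe guselkumab's safety. A single-arm study has no control group carrying the same run-in events, so the reader of the table cannot subtract them.

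The date rules add an inconsistency. The general definition starts at adenosine, and every rule for incomplete dates starts at guselkumab. The completeness of the recorded date can then decide whether a run-in event is counted.

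**Working it through.** The documents state no AE rate, so there is no plan figure to reproduce. The check covers the window, the possible effect on incidence, and the date rules.

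**1. Where the window opens.** Section 5.6.2 does not itself say first infusion or S2. That comes from Appendix 2, which ties safety capture to the first CFR at S2. With S2 14 to 28 days before Week 0, the window opens 14 to 28 days before guselkumab.

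**2. Added window length.** The window from first guselkumab is the study day of last dose plus 84 days, using the target days in SAP Table 2. Added length is run-in days divided by that window.
- Last dose at Week 28 (Day 197): 197 + 84 = 281 days. 14/281 = 5.0%; 28/281 = 10.0%.
- Last dose at Week 4 (Day 29): 29 + 84 = 113 days. 14/113 = 12.4%; 28/113 = 24.8%.
- Single dose (Day 1): 1 + 84 = 85 days. 14/85 = 16.5%; 28/85 = 32.9%.

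**3. Possible effect on incidence.** The SAP reports participants with at least one occurrence, so window length does not translate directly. Assume a constant AE rate λ per person-year, equal before and after dosing. The values of λ are an assumption. Then P(at least one) = 1 − exp(−λ × weeks/52). Each range is for a run-in of 2 to 4 weeks.

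| λ | 40 weeks: without → with run-in | 12 weeks: without → with run-in |
|---|---|---|
| 1 | 53.7% → 55.4-57.1% | 20.6% → 23.6-26.5% |
| 2 | 78.5% → 80.1-81.6% | 37.0% → 41.6-46.0% |
| 3 | 90.1% → 91.1-92.1% | 50.0% → 55.4-60.3% |

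For example, with λ = 2: 1 − exp(−2 × 40/52) = 78.5%; 1 − exp(−2 × 42/52) = 80.1%; 1 − exp(−2 × 44/52) = 81.6%.

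**4. Date rules side by side.** Take S2 on 13 February 2023 and Week 0 on 5 March 2023, a gap of 20 days.
- AE dated 23 February: after adenosine, so a TEAE under the general definition.
- The same AE recorded only as February 2023: the month precedes the treatment month, so the matrix imputes 1 February and labels it as before treatment start. It is not a TEAE under 5.6.2 or 5.6.2.1.1. The imputed date also precedes S2, so it would fail an adenosine anchor too.

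To see how often this could arise, 730 consecutive Week 0 dates (starting 1 July 2021) were enumerated. With the onset day missing, the share of run-in days falling in a calendar month before Week 0 is 24.7% for a 14-day gap, 36.2% for 21 days and 47.7% for 28 days. The remaining days share the Week 0 month. The matrix sets those to the earlier of TRTSDT and the AE resolution date.

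The rules also differ from each other. For an AE in the Week 0 month that resolved before the first dose, the clause in 5.6.2 excludes it and 5.6.2.1.1 includes it.

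**The case against.** The strongest reply is that opening the window at adenosine is disclosed and reasonable. Appendix 2 gives the reason: intravenous adenosine carries its own risk. That stands, and capture from S2 should be kept. But Appendix 2 uses this reason to justify the safety analysis set. It does not explain why run-in events should count in the guselkumab rate.

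A second reply is that the endpoint's wording says who is counted, not when, and that protocol section 9.4.4 summarises AEs with no treatment-emergent restriction. This is fair: the SAP does not breach an explicit protocol window. Reading the endpoint as post-dose is an interpretation. It fits the rest of the SAP, though: section 5.1.1 takes first dose to mean guselkumab, exposure in 5.6.1 runs from first to last guselkumab dose, and laboratory baseline is Week 0.

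Third, Appendix 2 expects the safety set to exceed the FAS, which suggests an adenosine-exposed population was intended. As written, requiring both adenosine and guselkumab, the set cannot exceed the FAS. The intent is therefore unclear and should be settled at the same time.

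A reader might infer three stronger claims that the documents do not support.
- **That all run-in complaints are counted.** Expected adenosine effects are excluded. SAP Appendix 6 also ties AE documentation to onset on or after Baseline, which conflicts with protocol 8.3.1, so the number of run-in events reaching the tables is uncertain.
- **That the adenosine signal is lost.** Onset dates stay in the data, SAEs are listed, and table layouts sit in a separate specifications document that is not available here.
- **That short exposures were common after the 31 May 2023 termination.** No document gives doses received per participant.

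**Conclusion.** The point holds as a definitional mismatch in a descriptive secondary endpoint, plus a real conflict in the date rules. Followed as written, the SAP lets AEs with onset 14 to 28 days before any guselkumab into the guselkumab AE rate, and it can classify the same event differently depending on whether the onset day was recorded.

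The size is modest for participants with full follow-up: 5 to 10% more window and, at an assumed 2 AEs per person-year, about 2 to 3 percentage points on the chance of at least one TEAE (78.5% to 80.1-81.6%). It is larger for short exposure, up to 16 to 33% more window after a single dose. It would be wrong to read 5 to 33% as the inflation of AE incidence. Those figures are calendar time, and the incidence effect rests on an AE rate the documents do not supply. The date-rule conflict touches only run-in AEs with incomplete dates. The primary analysis is unaffected.

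**What to change.** Keep capturing safety from S2, and define two periods by onset date:
1. **Adenosine run-in:** from first adenosine to before first guselkumab, tabulated separately.
2. **Guselkumab-emergent:** from first guselkumab dose to the end of window already stated in SAP 5.6.2.

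Use only period 2 for the guselkumab AE rate and for TEAEs of special interest. The latter agrees with protocol section 8.3.6, which concerns events after the first guselkumab administration. Tie the partial-date clause in 5.6.2, section 5.6.2.1.1 and the imputation matrix to the first-guselkumab anchor, and remove the same-month disagreement between them. State whether the safety set requires both agents or either.

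If adenosine events at Weeks 0, 16 and 32 are to be shown, identify them by onset relative to the infusion where date and time allow. Protocol Appendix 13 describes causality only as related or not related to study treatment, so no adenosine attribution field can be relied on.

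Cost: SAP wording, one period flag and one extra table. AEs are collected from consent, so the period split needs no new data.
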